There is a critical gap in the treatment of Juvenile Idiopathic Arthritis (JIA) wherein a majority of school-age children experience sleep deficiency, pain, and reduced health-related quality of life even with advances in medical management of the disease. Sleep deficiency, including inadequate quantity and poor quality, is a serious public health problem, is common and highly comorbid in JIA, with an estimated 20 to 25% diagnosed with insomnia during adolescence. Despite the pervasiveness of sleep deficiency in JIA, children receive no training in self-management strategies (activation, motivation, self-efficacy) that can help empower them to improve sleep quantity and quality before transitioning into adolescence. Lack of sleep self-management interventions in JIA represents an important problem because these children are more vulnerable to the long-term consequences of poor sleep, poorer health-related quality of life, and increased healthcare utilization. Further, studies in other chronic health conditions show that sleep deficiency is associated with lack of self-monitoring and goal setting - important components of self-management. Clinical resources to address sleep deficiency in JIA are not available, creating a significant unmet clinical need.

In considering the multiple needs of these children and parents, successful interventions will need to target self-management skills and be delivered to families in an accessible format. Based on the experiences of our team in developing and testing technology-based pain self-management interventions for children with chronic conditions and their families, and conducting usability studies for such tools, we hypothesize that this approach will also be effective for delivering a sleep self-management intervention for children with JIA and their parents. We aim to develop and test a technology-based sleep self-management intervention delivered for 8-to-13 year-old children with JIA and their parents. Initial feasibility, acceptability, and efficacy of the newly developed sleep self-management intervention will be tested in a pilot randomized controlled trial comparing the active intervention against standard care with a sample of 60 children with JIA and their parents. Sleep will

be measured using actigraphy, sleep diaries, & self-report measures. Problem-solving skills, motivation, beliefs about sleep, and sleep self-efficacy also will be measured before and after the intervention is applied.

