The testing of the online modules are expected to take 45-60 minutes.

Aims 1 & 2 (total 6 to 9 months)

Participate in 2 to 3 interviews at a convenient time and place (10 JIA parents and children)
 
 ○ interview questions would explore perceptions of poor sleep, facilitators and barriers to sleep, preferences and attitudes about technology to promote better sleep, the type of technology features you and your child would or would not like, and what features would make sleep health tools acceptable to JIA children and parents. ○ Each interview will take 45-60 minutes, and would be audio-recorded 	Sept 2018- May 2019

Test the online sleep-based program your own smartphone, tablet, or computer (5 JIA parents and children).
 
 ○ We would video record participants while interacting with the online modules and rating the usability and satisfaction of the online modules. We would also ask participants to describe what it is like having JIA and sleep problems. ○ We would like to share this video recording in an online intervention we want to develop to help children with JIA self-manage their sleep. See aim 3. Participants will have the option of opting out of the video recording. Participants will have an option to opt out of the videotaping. ○ We anticipate that the testing of the online modules would take 45-60 minutes. 	April 2019- August 2019

Aim 3: A pilot feasibility RCT (Active treatment group [SLEEPSMART online module] vs. control group) is proposed to test the feasibility, acceptability, and initial efficacy of the new 6-week sleep self-management intervention with 60 children with JIA (8 to 13 years) and their parents. Outcome assessments will occur at baseline (T1), immediately post intervention (8 weeks; T2), and 1 month post-intervention (T3). **Aims 3 will occur after Aims 1 and 2 are complete and will require a total of 3 months.**

Following completion of baseline assessments, participants will be randomized to one of two treatment groups (Active treatment [SLEEPSMART] or control group). **Active treatment group will include 30 JIA children who will be randomized to the online sleep intervention (SLEEPSMART). Control group will include 30 JIA children who will not receive the online SLEEPSMART intervention.**

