A blocked randomization scheme will be generated using an online program will be used to derive randomization assignment, programmed in the internet sleep intervention, and not accessible to study investigators. Enrolled participants will be continuously randomized

T1 BASELINE ASSESSMENT

A member of the research team will connect with eligible and interested participant children and their parent at convenient time, will talk about the purpose of the study, and obtain consent from parent/caregiver participants (see SLEEPSMART Consent in Appendix A). Child assent will then be obtained and copies of both documents given to the parent (see SLEEPSMART Assent in Appendix A).

After consent and assent, JIA children and their parent will be given a link with the electronic instruments preloaded and instructed to complete the instruments to the best of their ability. If questions arise, a member of the research team will answer as needed. This technique was successfully used in [name] and [name]'s prior intervention studies. The surveys for T1, T2, and T3 will take 30 to 35 minutes to complete.

**Table 1. Summary of T Assessments – All T1, T2, and T3 unless otherwise indicated
(T1 [Baseline], T2 [immediately post intervention], T3 [1 month post intervention])**

Parent Items	Estimated Time (minutes)/Assessment	Child Items	Estimated Time (minutes)
Demographics (age, gender, race, ethnicity, income; child age, race, ethnicity; medications) Childhood assessment questionnaire	5 T1 T1		
Self-management measures Self-efficacy to Manage Chronic Disease Scale Decision Balance sheet Goal setting (# and types of goals created of goals tracked and rate of goals) Credibility/Expectancy Questionnaire	<5	Self-management measures Child Self-efficacy Scale Patient activation measure Index of self-regulation Goal setting (# and types of goals created of goals tracked and rate of goals) Sleep problems questionnaire	<5
SYMPTOMS PROMIS 29 profile PROMIS Sleep disturbance -adult PROMIS sleep-related impairment	<5	SYMPTOMS PROMIS Peds Profile (physical function, anxiety, depression, fatigue, peer relationships, pain interference). PROMIS Sleep disturbance PedsQL Multidimensional Fatigue	10

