Submissions and progress will be monitored by a member of the research team, who will send email, call or text with reminders (whichever the family prefers) and answer questions as needed, review progress, and help problem solve any technology issues or barriers to implementing skills. This online structure and feedback process is modeled after the work by [name], Co-I on this grant, who has successfully implemented web-based interventions with parents and children.

T2 – IMMEDIATELY FOLLOWING INTERVENTION ASSESSMENT

At the end of the 6-week SLEEPSMART intervention, for both the treatment and control groups will be mailed actiwatches, and parents and children will wear for 10 days. They will also complete the daily sleep

diary as described before. Actigraphs and sleep diaries will be returned via prepaid envelopes. Plus the above questionnaires in Table 2.

T3 – 1 MONTH following baseline

For both the treatment and control groups, activewatches will be mailed to parent/child participants to wear for 10 days. They will also complete the daily sleep diary as described before. Actigraphs and sleep diaries will be returned via prepaid envelopes. Parents and children will individually complete the instruments/research items below, nearly identical to T0 baseline visit with the exception of removing the demographic questionnaire, and use of health care utilization survey (exit) for parents and the SLEEPSMART Acceptability Questionnaire. The parent/caregiver will be given a link with the electronic instruments preloaded and instructed to complete the instruments to the best of their ability. If questions arise, a member of the research team will answer as needed. After completing the below listed activities, parent and child participants will interviewed together using semi-structured interview questions to assess participant acceptability of the SLEEPSMART Study.

--	--	--	--

5.2 Data variables. Describe the specific data you will obtain (including a description of the most sensitive items). If you would prefer, you may upload a list of the data variables to the **Supporting Documents** SmartForm instead of describing the variables below.

Screening

Parent report of yes to either of the following questions: “does your child has difficulty with sleep quality and/or does poor sleep impact your child’s day-to-day function (school, interacting with peers, hobbies)?” **Pediatric Sleep Questionnaire (PSQ) Sleep Related Breathing Disordered Scale**

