22-item using 3 point scale (yes = 1, no= 0, don’t know = missing). Number “yes” items divided by total number of items responded, with scores ranging from 0-1. Scores >0.33 considered positive and suggestive of high risk for a pediatric sleep-related breathing disorder.

Does your child currently receive psychological therapy?

Enrolled subject data to be collected

Concept	Measure
Demographics	Parent-report survey includes information about parental characteristics (age, gender, education, race, ethnicity, household income) and child characteristics (age, gender, grade level, race, ethnicity, JIA type, and medications). Child Health Assessment Questionnaire -parent report measure that assesses daily activities and functional impairment due to chronic pain in child.
Self-Management Measures (treatment group only)	Self-Efficacy - 9-item parent & 5-item children report of their confidence in carrying out sleep-related behaviors using 10-point Likert scale (1=not confident at all, 10=totally confident). Higher scores indicate higher self-efficacy. Index of self-regulation - 12-item parents & child report of motivation (recondition, stimulus control, behavioral monitoring) Patient activation measure - 13-item parent & child report of knowledge, skill, & confidence for self-management. Goal Setting: engagement in goal setting will be tracked on the SLEEPSMART web-based application using # and type of goals created; # of goals tracked; and rate of goal completion. Sleep Problem questionnaire- 4 item child report of their readiness to change their sleep habits. Credibility /expectations Questionnaire: 6-item parent report questionnaire to rate treatment expectancy

Sleep	
	Child Sleep Habits Questionnaire (CSHQ) 45-item retrospective report of child sleep habits over typical week using 3 point Likert scale. Higher scores indicate greater likelihood of sleep disturbance, with >41 as the cut-point for clinically significant sleep disturbance. Eight sleep subscales include bedtime resistance, sleep onset delay, sleep duration, sleep anxiety, night awakenings, parasomnias, sleep-disordered breathing, and daytime sleepiness.
	Children's /Adolescent Sleep Wake Scale – 25-item child report measure of sleep quality over the last month; includes 5 domains: going to bed, falling asleep, maintaining sleep, reinitiating sleep, and returning to wakefulness. A total score indicates overall perception of sleep quality

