Actigraphy	Actiwatch 64 Small wrist watch that measures body movement and estimates of total sleep time, amount of wake, sleep quality, bedtime and waketime variability.
Sleep diary	Electronic daily sleep and pain diary-children and parents will complete an electronic sleep diary twice a day for 10 days. Children and parents will complete the diary at bedtime and upon waking (what time you went to bed, wake up, # and duration of night awakenings), events that may disrupt your sleep (anxious about a test; hobbies [music recital, basketball game, school event], parent out of town, fight with a friend, homework, sickness).

Below questionnaires to be completed by treatment group only:

Treatment Evaluation Inventory and End of Study Survey **Acceptability Survey** only the treatment group will complete this survey. 11-item survey to be used in post-intervention interview with parent and child. Survey includes 6 open-ended questions and 5 Likert scale questions (1=strongly disagree, 5=strongly agree). Items assess participant acceptability of various components of the SLEEPSMART Study.

5.3 Data sources. For all types of data that you will access or collect for this research: Identify whether you are obtaining the data from the subjects (or subjects' specimens) or whether you are obtaining the data from some other source (and identify the source).

If you have already provided this information in Question 5.1, you do not need to repeat the information here.

Data will be obtained from the child and parents in the form of:

Aims 1 & 2: semi-structured interviews, & videotaping, and testing of the REDCap SLEEPSMART Website use – site tracks unique ID logon date, time, duration;

Aim 3: surveys (REDCap), sleep diaries (REDCap), and wrist watch. REDCap SLEEPSMART Website use – site tracks unique ID logon date, time, duration.

The CRA at SCH will collect information from the child's medical record (name, age, sex, phone number, address), JIA form (disease duration, onset of symptoms, JIA type, active or inactive disease). The research staff at CHOP will not collect this information, rather parents will complete demographic survey that includes child age, gender, disease duration, JIA type, and active or inactive disease.

5.4 Retrospective/prospective.

For all types of data and specimens that you will access or collect for this research:

Describe which data are:

- Retrospective (i.e., exist at the time when you submit this application)

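### Section 5.2 labels the whole self-management block treatment-group-only, although three of its scales are secondary outcomes to be compared with usual care; if the label is followed at T2 and T3, that comparison cannot be made

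*Combined protocol and SAP*

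**What the plan says.** In section 5.2 (Data variables), the list of data for enrolled subjects opens the self-management block with "Self-Management Measures (treatment group only". Six instruments sit under that heading: self-efficacy, index of self-regulation, patient activation measure, goal setting, the Sleep Problem Questionnaire and the credibility/expectancy questionnaire.

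Section 1.5 (aim 3) and the Research Strategy (Aim 2) both name child and parent activation, motivation and self-efficacy as secondary outcomes. Aim 2 of the Research Strategy places them among the outcomes for which treated and usual-care children will be compared to obtain effect sizes. Its Data Analysis Plan examines secondary outcomes by GEE, over time and between groups, with interactions and contrasts. Its Measurement Plan assesses both groups at T1, T2 and T3.

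In section 5.1, Table 1 is titled "All T1, T2, and T3 unless otherwise indicated". Its child column lists "Child Self-efficacy Scale Patient activation measure Index of self-regulation" with no exception for time or arm. Its parent column lists a self-efficacy scale but neither self-regulation nor activation. On timing, section 5.1 says "Following completion of baseline assessments, participants will be randomized".

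**The concern.** A secondary outcome that is to be compared between arms must be measured after baseline in both arms. The section 5.2 heading, read as written, says that it will not be. A coordinator who builds the T2 and T3 surveys from section 5.2 would leave the scales out for controls. One who builds them from Table 1 would include them.

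The stake is the randomised comparison for activation, motivation and self-efficacy. Without control follow-up, the only result for these scales is a pre-post change in the treated arm, which mixes any intervention effect with retest and time effects. The between-group effect sizes meant to inform the future trial would be missing for these scales, and follow-up values not collected on time cannot be recovered.

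Secondary-outcome status alone does not settle this, because technology use is also a secondary outcome and exists only in the treated arm. What settles it is the planned comparison with usual care.

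**Working it through.** No figure in the plan is specific to this point. The check has two parts: what each place says about arms, and what the planned model can estimate under each reading.

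**What each place says**

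| Place | On arms | Weight |
|---|---|---|
| 5.2, block heading | Treatment arm only, all six instruments | Explicit |
| Research Strategy, Aim 2 and Data Analysis Plan | Comparison with usual care; between-group terms | Explicit, and the only analysis plan given |
| Research Strategy, Measurement Plan | Both groups at T1, T2, T3 | Explicit |
| 5.1, Table 1 | No arm limit on the child scales or parent self-efficacy | Implied: it also lists the acceptability inventory with no arm limit, which 5.2 restricts to the treated arm |
| 5.1, T2 paragraph | Both groups, but the questionnaires are those of Table 2 above | Implied: the Table 2 above it lists intervention modules, not instruments |
| 5.1, T3 paragraph | "For both the treatment and control groups, activewatches will be mailed to parent/child participants"; instruments "nearly identical to T0 baseline visit with the exception of removing the demographic questionnaire" | Suggestive: the both-groups phrase governs the actigraphs, and the questionnaire sentence names no arm |
| 1.8, Background | "motivation, beliefs about sleep, and sleep self-efficacy also will be measured before and after the intervention is applied" | Suggestive: also fits a pre-post measure in treated families |
| 5.2, later list | "Below questionnaires to be completed by treatment group only", covering the acceptability instruments | Suggestive: it need not repeat what the block heading already restricts |

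Since allocation follows T1, all families complete baseline before an arm exists. The label can remove only the control T2 and T3 assessments.

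**Records per scale**

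Inputs from the Research Strategy (Power): 60 dyads enrolled, 15% attrition, 50 projected (25 per group). Check: 60 × 0.85 = 51, which agrees with 50 after rounding.

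- Both arms at all times: 50 × 3 = 150 dyad-assessments, of which 25 × 2 = 50 are control follow-up.
- Label followed at T2 and T3: 25 × 3 + 25 = 100, of which 0 are control follow-up.

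**Estimability**

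Write the arm-by-time mean as b0 + b1·arm + b2·T2 + b3·T3 + b4·arm·T2 + b5·arm·T3. The planned contrasts are b4 and b5, the differences in change from baseline.

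- All six cells observed: rank 6; b4 and b5 are estimable.
- Label followed: four cells remain, namely control T1 (b0), treated T1 (b0 + b1), treated T2 (b0 + b1 + b2 + b4) and treated T3 (b0 + b1 + b3 + b5). The rank is 4. Only the sums b2 + b4 and b3 + b5 are identified, so time cannot be separated from treatment.

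More dyads do not help, because the missing cells stay empty. Nor does the planned multiple imputation: with no control value observed at T2 or T3, imputed values would come from assumption alone.

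**Items involved (counts from section 5.2)**

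- Child: 5 + 12 + 13 = 30, or 34 with the 4-item Sleep Problem Questionnaire.
- Parent: 9 if only self-efficacy is completed, or 9 + 12 + 13 = 34 if self-regulation and activation are included.

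**The case against.** The best defence is that the label was meant for only part of the block. Goal setting is tracked on the intervention website, and the credibility/expectancy questionnaire rates treatment expectancy; both fit a treated-arm limit. This is plausible and shapes the fix, but the label sits on the heading and so covers the outcome scales as well.

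A second defence is that the explicit both-arm statements come from the Research Strategy, which uses another intervention name and differs from the IRB form on age range and T3 timing. Within the IRB form, the evidence for both arms is weaker, as the table above shows. That stands: a reader might infer that the whole IRB form contradicts the heading, and it does not. However, section 1.5 of the form names the same secondary outcomes, Table 1 sets no arm limit, and the form contains no other analysis plan.

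Third, for parents Table 1 and section 5.2 disagree on whether self-regulation and activation are collected at all, not only on the arm. That is correct and needs its own answer.

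A reader might also infer that control follow-up will be lost, or that the trial's main efficacy comparison is at risk. The documents support neither. Section 5.1 describes T2 and T3 for both groups, so the surveys may already be built correctly. The primary outcomes (actigraphy sleep duration, sleep quality, feasibility/acceptability) are outside this block.

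**Conclusion.** The contradiction is real: the section 5.2 heading cannot stand beside the planned between-group analysis of self-efficacy, motivation and activation. Its consequence is conditional. If the heading is followed at T2 and T3, control follow-up for each of these scales falls from a projected 50 dyad-assessments to none, and neither group-by-time contrast nor any follow-up between-group effect size can be estimated. If the surveys follow Table 1 for both arms, nothing is lost for the scales it lists. The counts assume the plan's projected 25 completers per group; the loss of estimability does not depend on sample size. This concerns secondary outcomes in a pilot, and it should be corrected because the correction is cheap and the loss would be permanent.

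**What to change.** - Remove the treatment-only label from the block heading in section 5.2.
- State that self-efficacy, index of self-regulation and patient activation are collected in both arms at T1, T2 and T3.
- Limit the label to website-tracked goal setting and, if so intended, the credibility/expectancy questionnaire.
- State which arm completes the 4-item child Sleep Problem Questionnaire.
- Settle whether parents complete the self-regulation and activation scales: section 5.2 and the Research Strategy measures table say yes, while the parent column of Table 1 omits them.
- In the T2 paragraph of section 5.1, correct the questionnaire pointer from Table 2 to the assessment table, Table 1.

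The cost is a few extra survey minutes for control families at T2 and T3: 30 or 34 child items, and 9 to 34 parent items. Table 1 allows under 5 minutes for each self-management block. If the REDCap surveys already follow Table 1, the change is to wording only.

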6.1 Involvement of minors. Does your research include minors (children)?

Minor or child means someone who has not yet attained the legal age for consent for the research procedures, as described in the applicable laws of the jurisdiction in which the research will be conducted. This may or may not be the same as the definition used by funding agencies such as the National Institutes of Health.

In Washington State the generic age of consent is 18, meaning that anyone under the age of 18 is considered a child.

There are some procedures for which the age of consent is much lower in Washington State. See the [WORKSHEET: Children](#) for details.

The generic age of consent may be different in other states, and in other countries.

No → If no, go to [Section 8](#).

Yes → If yes, provide the age range of the minor subjects for this study and the legal age for consent in your population(s). If there is more than one answer, explain.

8-13 YEARS

Don't know → This means is it not possible to know the age of your subjects. For example, this may be true for some research involving social media, the Internet, or a dataset that you obtain from another researcher or from a government agency. Go to [Section 8](#).

6.2 Parental permission. **Parental permission** means actively obtaining the permission of the parents. This is not the same as "passive" or "opt out" permission where it is assumed that parents are allowing their children to participate because they have been provided with information about the research and have not objected or returned a form indicating they don't want their children to participate.

a. Will you obtain parental permission for:

All of your research procedures

→ Go to [question 6.2b](#).

None of your research procedures

→ Use the table below to provide your justification, and skip question 6.2b.

Some of your research procedures

→ Use the table below to identify the procedures for which you will not obtain written parental permission.

Be sure to consider all research procedures and plans, including screening, future contact, and sharing/banking of data and specimens for future work.

Children Group ¹	Describe the procedures or data/specimen collection (if any) for which there will be NO parental permission	Reason why you will not obtain parental permission	Will you inform them about the research? ²	
			YES	NO
N/A	N/A			
				
				

[figure not shown]

Table footnotes

1. If your answer is the same for all children groups or all procedures, you can collapse your answer across the groups and/or procedures.

2. Will you inform them about the research beforehand even though you are not obtaining active permission?

b. Indicate by checking the appropriate box(es) your plan for obtaining parental permission

Both parents, unless one parent is deceased, unknown, incompetent, or not reasonably available; or when only one parent has legal responsibility for the care and custody of the child

One parent, even if the other parent is alive, known, competent, reasonably available, and shares legal responsibility for the care and custody of the child.

This is all that is required for minimal risk research.

If you checked both boxes, explain:

Research is minimal risk, one parent will provide consent.

6.3 Children who are wards. Will any of the children be wards of the State or any other agency, institution, or entity?

→ If yes, an advocate may need to be appointed for each child who is a ward. The advocate must be in addition to any other individual acting on behalf of the child as guardian or *in loco parentis*. The same individual can serve as advocate for all children who are wards.

Describe who will be the advocate(s). Your answer must address the following points:

Background and experience

Willingness to act in the best interests of the child for the duration of the research

Independence of the research, research team, and any guardian organization

